6.14.2. Adverse Events

Adverse events are recorded in the eCRFs. Each AE will be coded to system organ class (SOC) and PT using the Medical Dictionary for Regulatory Activities (MedDRA) version that is current at the time of database lock. Severity of AEs is recorded as mild, moderate, or severe.

A TEAE is defined as an event that either first occurred or worsened in severity after the first dose of study treatment and on or prior to the last visit date during the analysis period. The analysis period is defined as the treatment period plus 30 days off-drug follow-up time.

Adverse events are classified based upon the MedDRA PT. The MedDRA Lowest Level Term (LLT) will be used in defining which events are treatment-emergent. The maximum severity for each LLT during the baseline period up to first dose of the study medication will be used as baseline. If an event with missing severity is preexisting during the baseline period, and persists during the treatment period, then the baseline severity will be considered mild for determining treatment-emergence (that is, the event is treatment-emergent if the severity is moderate or severe postbaseline and not treatment-emergent if the severity is mild postbaseline). If an event occurring postbaseline has a missing severity, then the event is considered treatment-emergent unless the baseline is severe, in which case the event is not treatment-emergent. The day and time for events where onset is on the day of the first dose of study treatment will both be used to distinguish between pretreatment and posttreatment to derive treatment-emergence. Should there be insufficient data for AE start date to make this comparison (for example, the AE start year is the same as the treatment start year, but the AE start month and day are missing), the AE will be considered treatment-emergent.

In general, summaries will include the number of patients in the safety population (N), frequency of patients experiencing the event (n), and relative frequency (that is, percentage; $n/N * 100$). For any events that are gender-specific based on the displayed PT, the denominator used to compute the percentage will only include patients from the appropriate gender.

For events of special interest, a more robust incidence rate, IR per 100 patient-years of observation (PYO) may be provided. Patient-years of observation will be calculated as the sum

of all patient observation time in the treatment group. For a patient with an event, the observation time will be censored at the event date; for a patient without the event, the observation time will be counted until the end of the analysis period.

PYO will be calculated as follows:

$$PYO = \sum_{pt \ w \ event} \frac{event \ start \ date - first \ trt \ dose \ date + 1}{365.25} + \sum_{pt \ w/o \ event} \frac{last \ observation \ date - first \ trt \ dose \ date + 1}{365.25}$$

IR will be calculated as follows:

$$IR = \frac{number \ of \ patients \ with \ event}{PYO} \times 100$$

For each IR provided, a Poisson Distribution 95% CI will be calculated. Treatment group comparisons will be provided based on the incidence rate difference (IRD) together with its 95% CI.

In an overview table, the number and percentage of patients in the safety population who experienced death, an SAE, any TEAE, discontinuation from the study due to an AE, permanent discontinuation from study drug due to an AE, or a severe TEAE will be summarized by treatment group.

The number and percentage of patients with TEAEs will be summarized by treatment group in 2 formats:

- by MedDRA PT nested within SOC with decreasing frequency in SOC, and events ordered within each SOC by decreasing frequency in the baricitinib 4-mg group;
- by MedDRA PT with events ordered by decreasing frequency in the baricitinib 4-mg group.

6.14.2.1. Common Adverse Events

Common TEAEs are defined as TEAEs that occurred in $\geq 2\%$ (before rounding) of patients in any treatment group including placebo. The number and percentage of patients with common TEAEs will be summarized by treatment using MedDRA PT ordered by decreasing frequency in the baricitinib 4-mg group.

The number and percentage of patients with TEAEs will be summarized by maximum severity by treatment using MedDRA PT ordered by decreasing frequency in the baricitinib 4-mg group for the common TEAEs. For each patient and TEAE, the maximum severity for the MedDRA level being displayed is the maximum postbaseline severity observed from all associated LLTs mapping to that MedDRA PT.

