6.14.5.6. Infections

Infections will be defined using all the PTs from the Infections and Infestations SOC as defined in MedDRA. Serious infection will be defined as all the infections that meet the SAE criteria.

The number and percentage of patients with TEAEs of infections, serious infections, and infections resulting in permanent study drug discontinuation will be summarized by treatment group using MedDRA PTs. The proportion of patients developing skin infections requiring antibiotic treatment by Week 16 will also be summarized on the overview of infections table.

The number and percentage of patients with TEAEs of infections by maximum severity will be summarized by treatment group using MedDRA PTs.

Treatment-emergent infections will be reviewed in context of other clinical and laboratory parameters via a listing (details see Compound level safety standards).

The TEAE infections will be further analyzed in terms of potential opportunistic infection, herpes zoster and herpes simplex. Summary of HBV DNA monitoring results and association between infection and neutropenia/lymphopenia will also be provided in the context of infections.

Opportunistic infection

To identify potential opportunistic infections (POIs), the following approach will be used:

- identifying the POIs using a list of MedDRA PTs (refer to the compound level safety standards).

Potential opportunistic infections is identified through these search approaches and may be combined in one list for medical assessment and final classification of whether the case met the modified Winthrop definitions for OI.

A final listing for OIs will be provided for the CSR and to assist the composition of patient narratives.

Herpes zoster

Cases of herpes zoster will be further classified as follows:

- localized or non-multidermatomal-involvement of the primary and/or adjacent dermatomes only
 - complicated – documented ocular (cornea or deeper structure; for example, iritis, keratitis, retinitis, etc.) or motor nerve involvement (e.g., palsy; post herpetic neuralgia [PHN] does not meet criteria for motor nerve involvement).
 - uncomplicated-localized or non-multidermatomal cases that are not complicated
- multidermatomal-involvement beyond primary and adjacent dermatomes (that is, >3 contiguous dermatomes) or involvement of two or more non-contiguous dermatomes

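### Minor: the TEAE maximum-severity table grades each patient over all LLTs under the preferred term, and does not limit the grade to the treatment-emergent ones

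*SAP*

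**What the plan says.** SAP Section 6.14.2 defines the event: "A TEAE is defined as an event that either first occurred or worsened in severity after the first dose of study treatment". It works at two levels of MedDRA. For classification, "Adverse events are classified based upon the MedDRA PT". For emergence, "The MedDRA Lowest Level Term (LLT) will be used in defining which events are treatment-emergent". The reference severity is also set term by term: "The maximum severity for each LLT during the baseline period up to first dose of the study medication will be used as baseline".

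The same section treats postbaseline severity and treatment-emergence as different things. Its rule for a pre-existing event with missing baseline severity that persists into treatment counts that event as "not treatment-emergent if the severity is mild postbaseline". An event can therefore have a postbaseline severity without being a TEAE.

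Section 6.14.2.1 then plans the table for common TEAEs: "The number and percentage of patients with TEAEs will be summarized by maximum severity by treatment using MedDRA PT". The grade shown for each patient and TEAE is set by this rule: "the maximum severity for the MedDRA level being displayed is the maximum postbaseline severity observed from all associated LLTs mapping to that MedDRA PT".

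Section 6.14.5.6 plans a table of the same kind for infections: "The number and percentage of patients with TEAEs of infections by maximum severity will be summarized by treatment group using MedDRA PTs". It gives no rule of its own for the maximum.

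**The concern.** The table is meant to show how severe the treatment-emergent events were. Under the written rule, whether a patient is in a preferred-term row depends on treatment-emergent LLTs, but the grade depends on every LLT under that term with a postbaseline severity. The two sets differ when a patient has a pre-existing LLT that continues without worsening and also a new or worsened LLT under the same term. The pre-existing severity is then credited to the TEAE.

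What is at stake is the severity breakdown in a descriptive safety table. A reader of that table takes a severe entry to mean that a new or worsened event was severe.

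**Working it through.** The SAP gives no figure to reproduce on this point, so the check is a trace of the written rules.

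**Inputs.** Severity has three levels: mild, moderate and severe (Section 6.14.2). Emergence and baseline severity are set for each LLT (Section 6.14.2). The displayed grade is the maximum over all LLTs under the preferred term (Section 6.14.2.1). The planned arms are 120 patients for each baricitinib dose and 240 for placebo (Section 5.1).

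**One patient, two LLTs under one preferred term.**
- LLT A is severe at baseline and still severe afterwards. It is neither new nor worsened, so it is not treatment-emergent.
- LLT B is absent at baseline, and new and mild afterwards. It is treatment-emergent.
- The patient is in the row because of B alone.
- Grade as written: max(severe, mild) = severe.
- Grade over treatment-emergent LLTs only: mild.

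**All combinations.** Let A be the postbaseline severity of the non-emergent LLT and B that of the emergent one.

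| A \\ B | mild | moderate | severe |
|---|---|---|---|
| mild | same | same | same |
| moderate | written rule higher | same | same |
| severe | written rule higher | written rule higher | same |

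The rules differ in 3 of the 9 cells, and in each of these the written rule gives the higher grade. It can never give a lower one, because a maximum over a larger set cannot be smaller. The 9 cells are not equally likely, so 3 of 9 is not a frequency. A need not be unchanged: an LLT that improved from severe to moderate would still lift a new mild event to moderate.

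**Size per affected patient.** A patient moved into the severe column adds 1/120 = 0.83 percentage points in a baricitinib arm, or 1/240 = 0.42 points in placebo. These use the planned randomised numbers; the safety population could be slightly smaller. They say nothing about how many patients would be affected.

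**Is the restriction stated elsewhere?** No other section of the SAP limits the maximum to treatment-emergent LLTs. Ongoing pre-existing conditions are expected in the data: Section 6.8.3 defines them, and Section 6.14.2 has a rule for events that persist into treatment.

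**The case against.** The strongest reply is that the sentence in Section 6.14.2.1 opens by making patient and TEAE the unit, and that the associated LLTs are then those belonging to that TEAE. A programmer who builds the table from records already flagged as TEAEs would get the intended grade. That reading is possible, and the SAP nowhere says outright that non-emergent LLTs are to be included. But nothing requires it. The LLTs that enter the maximum are identified by their mapping to the preferred term, and the severity is described as postbaseline, a word that this plan keeps apart from treatment-emergent. Two competent programmers could produce different tables.

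A second reply is that record selection may be fixed in the compound level safety standards, since the revision history says that details held in the standards were removed from the SAP. That may be so. However, Section 6.14.2.1 states its own rule for this table and does not refer to the standards, so the sentence should be right as it stands.

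A third reply is about reach, and it stands. The rule affects one kind of descriptive table. It leaves the counts of patients with the TEAE, the SAEs, the discontinuations and all efficacy results untouched. It needs two different LLTs under one preferred term, with the non-emergent one the more severe.

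**Conclusion.** The point holds as a minor one. On its literal wording, the rule in Section 6.14.2.1 can show a patient with a mild new event as having a severe TEAE. The shift is always upwards and can occur in any arm. Its frequency is unknown and probably low. The conclusion rests on reading the sentence as written, with no restriction supplied from a document outside the SAP.

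A reader might infer three stronger things, and the SAP supports none of them.

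- **That pre-existing severity in every arm masks a treatment difference.** Pre-existing severe disease alone regrades nobody. The patient must also have a new or worsened LLT under the same term, which arises after randomisation and may depend on treatment. The effect on a between-arm difference can therefore go in either direction.
- **That the table would contradict the severe-TEAE row of the overview table.** Section 6.14.2 lists that row without tying it to this rule, so no conflict is shown.
- **That severe counts would rise by a large factor.** Any such factor needs an assumed rate of truly severe events and an assumed number of regraded patients. The SAP gives neither.

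For infections, the point is only that Section 6.14.5.6 leaves the rule unstated. It does not cite Section 6.14.2.1, so carrying the rule over is an inference.

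**What to change.** In Section 6.14.2.1, insert the words treatment-emergent before LLTs, so that the maximum runs only over the treatment-emergent LLTs mapping to the displayed preferred term. In Section 6.14.5.6, state that the infection maximum-severity table uses the same rule.

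If the sponsor does intend every postbaseline LLT to count, the SAP should say so and the table should carry a footnote, so that a severe entry is not read as a severe new or worsened event.

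The cost is one amended sentence, one added sentence and a filter on the treatment-emergent flag, which Section 6.14.2 already requires to be derived. No other analysis changes.

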6.14.2.2. Serious Adverse Event Analyses

Consistent with the International Conference on Harmonisation (ICH) E2A guideline (1994) and 21 Code of Federal Regulations (CFR) 312.32 (a) (2010), a SAE is any AE that results in any one of the following outcomes:

- Death
- Initial or prolonged inpatient hospitalization
- A life-threatening experience (that is, immediate risk of dying)
- Persistent or significant disability/incapacity
- Congenital anomaly/birth defect

The number and percentage of patients who experienced any SAE will be summarized by treatment using MedDRA PT nested within SOC. Events will be ordered by decreasing frequency in the baricitinib 4-mg group within decreasing frequency in SOC. The SAEs will also be summarized by treatment using MedDRA PT without SOC.

An individual listing of all SAEs will be provided. A listing of deaths, regardless of when they occurred during the study, will also be provided.

6.14.2.3. Other Significant Adverse Events

Other significant AEs to be summarized will provide the number and percentage of patients who

- permanently discontinued study drug because of an AE or death;
- temporarily interrupted study drug because of AE;

by treatment using MedDRA PT nested within SOC. Events will be ordered by decreasing frequency in the baricitinib 4-mg group within decreasing frequency in SOC.

A summary of temporary interruptions of study drug will also be provided, showing the number of patients who experienced at least one temporary interruption and the number of temporary interruptions per patient with an interruption. Further, the duration of each temporary interruption (in days), the cumulative duration of dose interruption (in days) using basic descriptive statistics and the reason for dose interruption will be provided.

A listing of all AEs leading to permanent discontinuation from the study drug or from the study will be provided. A listing of all temporary study drug interruptions, including interruptions for reasons other than AEs, will be provided.

6.14.2.4. Criteria for Notable Patients

Patient narratives will be provided for all patients who experience certain “notable” events prior to data cutoff for the submission. See compound level safety standards for list of criteria.

6.14.3. Clinical Laboratory Evaluation

For the categorical laboratory analyses (shift and treatment emergent), the analysis period is defined as the treatment period plus 30 days off-drug follow-up time. The analysis period for the continuous laboratory analyses (e.g., change from baseline) is defined as the treatment period excluding off-drug follow-up time.

All laboratory tests will be presented using the International System (SI) and US conventional (CN) units. The performing central laboratory reference ranges will be used to define the low and high limits. Key results pertaining to the 4 key hepatic laboratory assessments (alanine aminotransferase [ALT], aspartate aminotransferase [AST], total bilirubin, and alkaline phosphatase [ALP]) will be included as a separate analysis to address the risk of liver injury as a special safety topic (see Section 6.14.5.1).

There is one special circumstance for laboratory values to be derived based on regularly scheduled, protocol-specified analytes. The low-density lipoprotein/high-density lipoprotein (LDL/HDL) ratio will be derived as the ratio of LDL cholesterol to HDL cholesterol. There are no central lab reference ranges for the LDL/HDL ratio.

The following will be conducted for the laboratory analytes collected quantitatively:

- **Box plots:** Values at each visit (starting at randomization) and change from last baseline to each visit and to last postbaseline measure will be displayed in box plots for patients who have both a baseline and at least 1 postbaseline visit. The last non-missing observation in the treatment period will be used as the last observation. Individual measurements outside of reference limits will also be displayed using distinct symbols overlaying the box plot. Original-scale data will be used for the display but for some analytes (for example, immunoglobulins) a logarithmic scale will be used to aid in viewing the measures of central tendency and dispersion. Unplanned measurements will be excluded. Descriptive summary statistics will be included below the box plot along with p-values resulting from between treatment comparison in change from last baseline to last observation. An ANCOVA model with explanatory term for treatment and the baseline value as a covariate will be used. These box plots will be used to evaluate trends over time and to assess a potential impact of outliers on central tendency summaries.
- **Treatment-emergent high/low analyses:** The number and percentage of patients with treatment-emergent high and low laboratory results at any time will be summarized by treatment group. Planned and unplanned measurements will be included. A treatment-emergent **high** result is defined as a change from a value less than or equal to the high limit at all baseline visits to a value greater than the high limit at any time during the treatment period. A treatment-emergent **low** result is defined as a change from a value greater than or equal to the low limit at all baseline visits to a value less than the low limit at any time during the treatment period. The Fisher's exact test will be used for the treatment comparisons.

For laboratory analyte measurements collected qualitatively, a listing of abnormal findings will be provided. The listing will include but not be limited to patient ID, treatment group, laboratory collection date, analyte name, and analyte finding. If needed by the safety physician/scientist, the number and percentage of patients with treatment-emergent abnormal laboratory results at any time will be summarized by treatment. Planned and unplanned measurements will be included. A treatment-emergent abnormal result is defined as a change from normal at all baseline visits to abnormal at any time postbaseline.

The listing of specific reference ranges used in analysis of laboratory data will be provided.

Note that additional analyses of certain laboratory analytes will be discussed within sub-sections of Section 6.14.5 pertaining to Special Safety topics (Section 6.14.5.1 for hepatic analytes, Section 6.14.5.2 for analytes related to hematological changes, Section 6.14.5.3 for analytes related to lipids, Section 6.14.5.4 for analytes related to renal function, and Section 6.14.5.5 for CPK).

6.14.4. Vital Signs and Other Physical Findings

For the treatment-emergent categorical analyses (shift and treatment emergent), the analysis period is defined as the treatment period plus 30 days off-drug follow-up time. The analysis period for the continuous analyses (e.g., change from baseline) is defined as the treatment period excluding off-drug follow-up time.

Vital signs and physical characteristics include systolic blood pressure (SBP), diastolic blood pressure (DBP), pulse, weight, and BMI. Original-scale data will be analyzed. When these parameters are analyzed as continuous numerical variables, unplanned measurements will be excluded. When these parameters are analyzed as categorical outcomes and/or treatment-emergent abnormalities, planned and unplanned measurements will be included.

The planned analyses described for the laboratory analytes in Section 6.14.3 will be used to analyze the vital signs and physical characteristics.

Table JAHM.6.8 defines the low and high baseline values as well as the criteria used to define treatment-emergence based on post-baseline values. The blood pressure and pulse rate criteria are consistent with the document *Selected Reference Limits for Pulse/Heart Rate, Arterial Blood Pressure (Including Orthostasis), and Electrocardiogram Numerical Parameters for Use in Analyses of Phase 2-4 Clinical Trials Version 1.3* approved on 29 April 2015 as recommended by the Lilly Cardiovascular Safety Advisory Committee (CVSAC).

Table JAHM.6.8. Categorical Criteria for Abnormal Treatment-Emergent Blood Pressure and Pulse Measurement, and Categorical Criteria for Weight Changes for Adults

Parameter (Units of Measure)	Low	High
Systolic Blood Pressure (mm Hg)	≤90 (low limit) and decrease from lowest value during baseline ≥20 if >90 at each baseline visit	≥140 (high limit) and increase from highest value during baseline ≥20 if <140 at each baseline visit
Diastolic Blood Pressure (mm Hg)	≤50 (low limit) and decrease from lowest value during baseline ≥10 if >50 at each baseline visit	≥90 (high limit) and increase from highest value during baseline ≥10 if <90 at each baseline visit
Pulse (beats per minute)	<50 (low limit) and decrease from lowest value during baseline ≥15 if ≥50 at each baseline visit	>100 (high limit) and increase from highest value during baseline ≥15 if ≤100 at each baseline visit
Weight (kilograms)	(Loss) decrease ≥7% from lowest value during baseline	(Gain) increase ≥7% from highest value during baseline

6.14.5. Special Safety Topics, including Adverse Events of Special Interest

In addition to general safety parameters, safety information on specific topics of special interest will also be presented. Additional special safety topics may be added as warranted. The topics outlined in this section include the protocol-specified AESI.

In general, for topics regarding safety in special groups and circumstances, patient profiles and/or patient listings, where applicable, will be provided when needed to allow medical review of the time course of cases/events, related parameters, patient demographics, study drug treatment and meaningful concomitant medication use. In addition to the safety topics for which provision or review of patient data is specified, these will be provided when summary data are insufficient to permit adequate understanding of the safety topic.

